6.5.3 Visit 3 – 6 m ± 2 weeks

- 6.5.3.1 Clinical history – recurrent thrombosis – malignancy.
- 6.5.3.2 Clinical PTS scores according to Villalta and CEAP. Bilateral leg circumference.
- 6.5.3.3 Assessment of functional venous obstruction by air-plethysmography.
- 6.5.3.4 Ultrasonographic assessment of postthrombotic changes, patency, and reflux⁴⁴⁻⁴⁷.
- 6.5.3.5 Quality of Life (QoL) assessment (Appendix 2).
- 6.5.3.6 D-dimer testing, INR, thrombophilia screening (if previously inconclusive).

6.5.4 VISIT 4 – 12 m ± 4 weeks

Telephone interview – recurrent thrombosis – malignancy.

6.5.5 VISIT 5 – 24 m ± 4 weeks

- 6.5.5.1 Clinical history – recurrent thrombosis – malignancy.
- 6.5.5.2 Clinical PTS scores according to Villalta and CEAP. Bilateral leg circumference..
- 6.5.5.3 Assessment of functional venous obstruction by air-plethysmography.
- 6.5.5.4 Ultrasonographic assessment of postthrombotic changes, patency, and reflux
- 6.5.5.5 Quality of Life (QoL) assessment (Appendix 2).
- 6.5.5.6 D-dimer, INR, thrombophilia screening (if previously inconclusive).

6.5.6 VISIT 6 – 36 m ± 4 weeks

Telephone interview – recurrent thrombosis – malignancy.

6.5.7 VISIT 7 – 48 m ± 4 weeks

Telephone interview – PTS screening – recurrent thrombosis – malignancy.

6.5.8 VISIT 8 – 60 m ± 8 weeks

- 6.5.8.1 Clinical history – recurrent thrombosis – malignancy.
- 6.5.8.2 Clinical PTS scores according to Villalta and CEAP. Bilateral leg circumference.
- 6.5.8.3 Ultrasonographic assessment of postthrombotic changes, patency, and reflux.
- 6.5.8.4 Assessment of functional venous obstruction by air-plethysmography.
- 6.5.8.5 Quality of Life (QoL) assessment (Appendix 2).

7 DEFINITIONS

7.1 Post-Thrombotic Syndrome (PTS)

7.1.1 The Villalta Score^{5;43}

PTS will be evaluated using the Villalta score, which scores PTS based on five symptoms and six objective signs (each item graded from 0 to 3):

Five symptoms: heaviness, pain (spontaneous or during deambulation), cramps, pruritus, and paresthesia.

Six signs: pretibial edema, induration of the skin, hyperpigmentation, new venous ectasia, redness, pain during calf compression

A total score of 5-14 indicates mild to moderate PTS, whereas a score of 15 or more indicates severe PTS. A lower limb venous ulcer indicates severe PTS regardless of the sum of the remaining signs and symptoms. The Villalta Score is quantitative and useful for longitudinal assessment of PTS.

7.1.2 The Clinical-Etiology-Anatomic-Pathophysiologic (CEAP) classification^{48;49}

This is a classification of Clinical (dermatological) signs, Etiology, Anatomic distribution and Pathophysiologic dysfunction:

Clinical signs	Class 0	No visible or palpable signs of venous disease
	Class 1	Teleangiectases or reticular veins
	Class 2	Varicose veins
	Class 3	Edema
	Class 4	a. pigmentation, eczema b. lipodermatosclerosis, atrophia blanche
	Class 5	Healed ulceration (and skin changes as defined above)
	Class 6	Active ulceration (and skin changes as defined above)
Etiological classification	Congenital, primary, secondary	
Anatomic distribution	Superficial, deep, or perforator, alone or in combination	
Pathophysiological dysfunction	Reflux or obstruction, alone or in combination	

7.2 Non-invasive assessment of veins

7.2.1 Deep vein thrombosis⁵⁰

7.2.1.1 Acute deep vein thrombosis

The principal criterion is inability to completely compress the vein lumen when examining the vein in the transverse plane. Other possible findings are distention of the vein, absence of flow, loss of phasic flow, and visualization of clot.

7.2.1.2 Chronic thrombosis and postthrombotic changes

Absence of complete incompressibility indicates residual thrombosis. Other postthrombotic features are wall-thickening and intraluminal hyperechoic structure.

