A National DVT Registry was established in North-America to analyze results in a large number of patients treated with CDT³⁸. This registry included 473 patients with documented lower extremity DVT treated with CDT, but follow-up data included only 287 patients who received 312 treatments. Thrombi subjected to lysis included either ilio-femoral vein thrombosis in 71% of cases and femoro-popliteal vein thrombosis in 25% of cases. The mean age of patients was 47.5 years and the mean duration of infusion was 53 h. All patients had six months of therapy with oral anticoagulants following CDT and many had heparin as well. Complete lysis was obtained in 31% of patients, 50-99% lysis in 52% and <50% lysis in 17%. Successful lysis was not related to location of the thrombus. The overall primary patency rate was 80% at 12 months, with better patency for ilio-femoral segments than the femoro-popliteal segments. Major bleeding complications occurred in 11% of patients; 39% of these at the venous insertion site, 13% were retroperitoneal hematoma. Minor bleeding events occurred in 16% of patients, again most often at the venous entry site. There was one fatal intracranial hemorrhage, one subdural hematoma, and 6 pulmonary emboli of which one was fatal. Thus, the overall mortality rate from lysis was 0.4%. There was no data on PTS.

If the PTS differs between standard therapy and thrombolytic therapy then the quality of life may differ between patients also. Comerota assessed health-related quality of life in patients after CDT therapy compared to a group of patients treated with standard anticoagulation therapy³⁹. The delayed functional outcome and wellbeing scores were significantly better in the thrombolytic therapy group. Although this study had some methodological shortcomings¹³, the findings are still suggestive that thrombolytic therapy may offer improved quality of life in patients who achieve successful thrombolysis.

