3 OBJECTIVES

3.1 PRIMARY OBJECTIVES

To investigate whether catheter-directed thrombolytic therapy for first-time acute DVT of the iliofemoral veins may:

- 3.1.1 increase patency rate at 6 months.
- 3.1.2 reduce the risk of PTS at 2 years.

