7.2.5 Assessment of venous patency

Assessment of venous patency will include compressibility, flow and functional venous obstruction.

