7.3 Evaluation of thrombolysis

Based on venography before and after CDT, thrombolysis will be graded by a scoring system³⁸. Score=0 indicates an open vein, score=1 a partly occluded vein, and score=2 a completely occluded vein.

Each of the following 7 venous segments will be given a grade (0-2): IVC, the common iliac vein, the external iliac vein, the common femoral vein, the proximal and distal superficial femoral veins, and the popliteal vein. A total thrombus score before and after lysis will be calculated by adding the 7 scores. The difference between the pre- and postlysis thrombus scores divided by the prelysis score gives the grade of thrombolysis. Grade I=<50%; grade II=50-90%, and grade III=complete thrombolysis

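### The follow-up ultrasound criterion for residual thrombosis (7.2.1.2) is inverted as written, and the lysis grades (7.3) leave four reachable scores without a grade

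*Protocol*

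**What the plan says.** **Compressibility.** For acute thrombosis, Protocol 7.2.1.1 says: "The principal criterion is inability to completely compress the vein lumen when examining the vein in the transverse plane". For the chronic phase, 7.2.1.2 says: "Absence of complete incompressibility indicates residual thrombosis". Section 7.2.5 says: "Assessment of venous patency will include compressibility, flow and functional venous obstruction". It gives no rule for combining the three and does not refer to 7.2.1.2. A primary objective (3.1) is to "increase patency rate at 6 months", and the 6-month visit (6.5.3) lists "Ultrasonographic assessment of postthrombotic changes, patency, and reflux".

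**Lysis grade.** Section 7.3 scores each of seven venous segments on venography: "Score=0 indicates an open vein, score=1 a partly occluded vein, and score=2 a completely occluded vein". The segment scores are summed before and after lysis, and the fall is expressed as a fraction of the pre-lysis total. The bands are "Grade I=<50%; grade II=50-90%, and grade III=complete thrombolysis". The scoring is attributed to reference 38, the North American registry. Section 2 summarises that registry as follows: "Complete lysis was obtained in 31% of patients, 50-99% lysis in 52% and <50% lysis in 17" percent.

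**The concern.** Both passages are operative outcome rules. Followed to the letter, one gives a wrong result and the other gives none.

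The chronic-phase criterion carries a double negative that turns it round. Follow-up ultrasound at 6, 24 and 60 months takes place in the chronic phase, and no other compressibility criterion is given for it. If an assessor or a case report form applied the sentence as it stands, healthy veins would be recorded as thrombosed and wholly incompressible ones as clear. That would corrupt the record of postthrombotic changes. It could also reach patency if the same criterion were used for the compressibility component.

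The lysis bands stop at 90% and resume at complete lysis. A patient between the two has no grade, so someone must choose one after seeing the result. Such patients had extensive thrombus and near-complete clearance, so they are relevant to procedural success (3.2.4) and markers of successful lysis (3.2.5).

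**Working it through.** No sample size, power or significance level enters this point, so there is no planning figure to reproduce.

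**Step 1. The two compressibility criteria compared.** Inputs: the wording of 7.2.1.1 and 7.2.1.2. There are three possible states.

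| State of the vein | 7.2.1.2, literal: residual thrombosis? | 7.2.1.1 logic: thrombosis? |
|---|---|---|
| Fully compressible | Yes | No |
| Partly compressible | Yes | Yes |
| Completely incompressible | No | Yes |

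Both extremes are reversed and the middle state agrees.

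**Step 2. Reachable lysis values.** Inputs from 7.3: seven segments scored 0, 1 or 2, so the total runs from 0 to 7 × 2 = 14; lysis = (pre − post) / pre.

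Take every pair with pre from 1 to 14 and post from 0 to pre. The number of pairs is the sum of (pre + 1) = 105 + 14 = 119. Applying the bands as written:

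- grade I (<50%): 56 pairs
- grade II (50–90%): 45 pairs
- grade III (complete): 14 pairs
- no grade: 4 pairs
- check: 56 + 45 + 14 + 4 = 119

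A pair falls in the gap when 0.90 < 1 − post/pre < 1, that is, 0 < post < 0.1 × pre. Since pre is at most 14, post must be below 1.4 and hence equal to 1, and pre must exceed 10:

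- 11 to 1: 10/11 = 90.9%
- 12 to 1: 11/12 = 91.7%
- 13 to 1: 12/13 = 92.3%
- 14 to 1: 13/14 = 92.9%

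A fall from 10 to 1 is exactly 90% and belongs to grade II. Rounding to whole percentages does not close the gap (91, 92, 92, 93). A pre-lysis score of at least 11 needs at least six involved segments, because five give at most 10. A post-lysis score of 1 means one partly occluded segment remains.

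**Step 3. After correction.** If residual thrombosis means failure to compress completely, the literal column of the table becomes No, Yes, Yes and matches 7.2.1.1. If grade II runs from 50% to below 100%, the four pairs join it (45 + 4 = 49), and all 119 pairs have exactly one grade.

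**The case against.** The sentence in 7.2.1.2 is almost certainly a slip of one prefix. The subsection just before it states the intended logic, and end-points are assessed by a vascular surgeon (6.5), who is unlikely to call a normal vein thrombosed. This stands as a reason to expect little actual harm. It does not make the written rule right, and a multi-center protocol should be usable as it reads.

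The link to primary patency is inferred. Section 7.2.5 neither cites 7.2.1.2 nor mentions residual thrombosis, and the visit schedule lists postthrombotic changes and patency as separate items. Compressibility could be recorded for patency without using the faulty sentence. This also stands, so the link is stated only as possible.

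A reader might infer that the literal rule would turn the expected 30-point patency benefit (80% against 50%) into harm. The documents do not support that. Those planning rates are for patency, which also includes flow and functional obstruction; the protocol gives no compressibility rates. Even if they were taken as the shares of fully compressible veins, the literal rule would label 80–100% of CDT veins and 50–100% of control veins as residual thrombosis, depending on how the rest split between partly compressible and completely incompressible. The CDT-minus-control difference could then lie anywhere from 80 − 100 = −20 to 100 − 50 = +50 points, so its sign is not determined. Nor does the error grow with recovery: the rule is binary, and partly and fully compressible veins get the same label.

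On the lysis grades, the gap is narrow, it leaves patients ungraded rather than misgraded, and the protocol does not define success by these grades. The segment scores allow the grade to be recalculated at any time. All of this stands and makes the second item minor.

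**Conclusion.** Both defects hold as errors in the current text.

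Section 7.2.1.2 is inverted at both extremes relative to 7.2.1.1. It may affect the compressibility component of 6-month patency. How many patients' status would change cannot be computed, because no combining rule and no compressibility rates are given and it is unknown whether anyone would apply the sentence literally. No size or direction of bias in the primary comparison should be claimed.

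Section 7.3 leaves 4 of 119 possible score pairs (90.9% to 92.9%) ungraded. The 4 of 119 counts possible scores, not expected patients; the protocol gives no distribution of pre-lysis scores. The measure is secondary and exists only in the CDT arm, so neither primary comparison is touched.

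The first item should be corrected because it may bear on a primary outcome. The second is a tidy-up that can be made in the same amendment.

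**What to change.** **7.2.1.2:** replace the sentence with: *Incomplete compressibility (inability to compress the lumen completely) indicates residual thrombosis.* This matches 7.2.1.1.

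**7.3:** set the bands as *Grade I: <50%; Grade II: 50% to <100%; Grade III: 100%.* This is consistent with the registry bands in section 2.

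The cost is two wording corrections in section 7, carried through to the ultrasound and venography case report forms. If follow-up ultrasounds have already been recorded, confirm which way compressibility was coded. Lysis grades already assigned can be recalculated from the segment scores. No change to sample size, visits or treatment follows.

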7.2.2 Flow

Using Doppler-ultrasound, flow will be graded as spontaneous flow, forced flow (on peripheral compression), and no flow (obstruction)³⁸. Flow will also be examined in supine position.

7.2.3 Reflux

Using Doppler-ultrasound and a distal inflation cuff with the patient in standing position, reflux is defined as reversal of the velocity curve after distal pneumatic decompression lasting longer than 0.5 second⁵¹⁻⁵³.

7.2.4 Assessment of functional venous obstruction

Venous obstruction will be assessed by using air plethysmography^{54;55}. The patients will lie supine with the calf elevated (by a cushion) to the level of the heart. An occlusion cuff will be placed proximally on the thigh, and a recording cuff with a pressure of 6 mmHg will be placed on the calf. The proximal cuff will be inflated to 50 mmHg for 1 min. A venous outflow curve will be recorded when this cuff is deflated, and maximum outflow can then be calculated (delta mm/sec). Low outflow rates indicate presence of functional venous obstruction. The procedure will be performed on both legs.

7.2.5 Assessment of venous patency

Assessment of venous patency will include compressibility, flow and functional venous obstruction.

7.3 Evaluation of thrombolysis

Based on venography before and after CDT, thrombolysis will be graded by a scoring system³⁸. Score=0 indicates an open vein, score=1 a partly occluded vein, and score=2 a completely occluded vein.

Each of the following 7 venous segments will be given a grade (0-2): IVC, the common iliac vein, the external iliac vein, the common femoral vein, the proximal and distal superficial femoral veins, and the popliteal vein. A total thrombus score before and after lysis will be calculated by adding the 7 scores. The difference between the pre- and postlysis thrombus scores divided by the prelysis score gives the grade of thrombolysis. Grade I=<50%; grade II=50-90%, and grade III=complete thrombolysis

7.4 Bleeding Complications

7.4.1 **Major bleeding** – any bleeding associated with a reduction in hemoglobin by ≥ 2 g/100 mL or bleeding requiring transfusion of ≥ 2 U pack red blood cells or whole blood or bleeding in a critical organ, intracranial, retroperitoneal or pericardial or bleeding contributing to death.

7.4.2 **Clinically relevant non-major bleeding** – overt bleeding not meeting criteria for major bleeding but satisfying a priori criteria defined by the safety monitoring committee including for example skin hematomas >100 cm², epistaxis lasting >5 min, being repetitive ($\geq 2/24$ h) or requiring intervention (packing, electrocoagulation), macroscopic hematuria – either spontaneous or lasting >24 h after instrumentation (catheter or surgery) of the urogenital tract, or any other bleeding type that is considered to have clinical consequences for the patient.

7.4.3 **Trivial bleeding** - all other overt bleeding episodes not meeting the criteria for clinically relevant bleeding.

7.5 Thrombophilia screening

Includes screening for antithrombin, protein C- and protein S deficiencies, factor V Leiden mutation, the prothrombin gene 20210GA allele variation and the methylene tetrahydrofolate reductase (MTHFR) mutation, homocystein, lupus anticoagulants and anticardiolipin antibodies.

8 STATISTICS

8.1 Sample size

Numerous studies indicate that conventional treatment, i.e., UFH or LMWH followed by oral anticoagulants is associated with PTS in more than 60-80% of the cases, whereas systemic thrombolytic therapy is associated with PTS in approximately 30% of the patients^{5;21;56}. More recent studies employing systematic use of elastic compression stockings suggest PTS in approximately 25% of the patients.¹¹ In the present study, we will assume that the rate of PTS after 2 years will be at least 25% in those allocated conventional therapy as compared with less than 10% in those given CDT. For patency after 6 m we assume that the rate is less than 50% in those allocated conventional treatment as compared with at least 80% in those given CDT. With a significance level of $\alpha \leq 5\%$ and a statistical power $(1-\beta)$ of $\geq 80\%$, we will need to randomize approximately 100 patients in each group.

Also as presented in our hypotheses, we assume that venous patency after 6 months occurs in less than 50% in those allocated conventional treatment as compared to at least 80% in those given adjunctive CDT. It may then be shown that with a significance level of 5% and a statistical power $\geq 80\%$, 76 patients must be included to test this short-term hypothesis. We plan to analyse patency rates after 6 months based on the first 100 patients with 6 months patency data. This analysis will be repeated when 200 patients have 6 months patency data.

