1 SYNOPSIS

Deep vein thrombosis (DVT) is a severe disease which may cause severe disability and which is sometimes fatal. Conventional treatment with low molecular weight heparin (LMWH) and oral anticoagulants is associated with some degree of long-term sequelae, i.e., post-thrombotic syndrome (PTS), in more than 60-80% of the patients. Systemic thrombolytic therapy reduces the risk of PTS, but is associated with an unacceptably high risk of bleeding complications, many being disabling or fatal. Catheter-directed thrombolytic (CDT) therapy is a novel treatment modality which has been introduced in many hospitals worldwide. Low dose fibrinolytic agents are delivered continuously and directly into the thrombus through a catheter until thrombus has dissolved. Although many, mostly small series, have suggested a beneficial effect of this costly treatment in terms of increased patency of the veins and improved short term functional outcome, there are no randomized clinical trials documenting its short and long-term efficacy and safety.

The present study is a randomized, open-label, multi-center clinical trial among hospitals in the Eastern and Southern Norway Health Authorities (Helse Øst and Sør). Patients with acute iliofemoral vein thrombosis will be randomized to either conventional treatment or CDT in addition to conventional treatment. Main outcome parameters are patency rates at 6 months and prevalence of PTS at 24 months. A number of secondary outcomes include bleeding complications, recurrent thrombosis, quality of life (QoL), markers of importance for successful lysis and recurrent thrombosis, and whether PTS is related to patency at the end of treatment.

Our main short-term hypothesis is that CDT of first-time acute DVT will increase patency of the affected iliofemoral vein segments after 6 months from <50% on conventional therapy to >80% after CDT. Our main long-term hypothesis is that CDT will improve long-term functional outcome, i.e., risk of PTS, assessed after 2 years, from >25% on conventional treatment to <10% after CDT. The estimated sample size is at least 100 evaluable patients in each group using a statistical significance (α) = 5% and a statistical power ($1-\beta$) = 80%.

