8.2 Statistical methods

All statistical analysis will be performed according to the intention-to-treat principle. If ineligible patients are mistakenly included, they may be excluded (ref Ferguson et al BMJ 2002), apart from this, no other post-randomization exclusions will be made. The effect of treatment will be determined using 2x2 tables with assessment of the difference between patent vessels and prevalence of PTS, relative risks, and odds ratios with 95% confidence limits. The prevalence of clinically relevant bleeding, PTS, vein anomalies, thrombophilia, recurrent DVT will be determined using point estimates with 95% confidence intervals. A stratification analysis will be carried out using the Mantel-Haenzel method. Differences in baseline characteristics may be adjusted for using a multivariate logistic model. This may be done if there are substantial differences between the two groups, and if the variable(s) is probably or certainly associated with the outcome measure, e.g., age and previous VTE. Missing data on end-point variables will be scored as previous score or last/worst score carried forward.

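### The 6-month patency hypothesis is set at 5% but analysed on 100 patients and again on 200 with no adjustment, so its type I error is 8.3% if either result counts

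*Protocol*

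**What the plan says.** The Synopsis names two main outcomes: "Main outcome parameters are patency rates at 6 months and prevalence of PTS at 24 months". Sections 3.1 and 4 give each its own primary objective and its own main hypothesis.

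Section 8.1 sizes the trial for PTS (25% against 10%) at about 100 per group. It then treats patency (50% against 80%) separately: "It may then be shown that with a significance level of 5% and a statistical power" of at least 80%, 76 patients are enough for that hypothesis. The analysis schedule follows directly: "We plan to analyse patency rates after 6 months based on the first 100 patients with 6 months patency data", and then "This analysis will be repeated when 200 patients have 6 months patency data".

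Section 8.2 plans 2x2 tables with differences, "relative risks, and odds ratios with 95% confidence limits". Neither section gives an adjusted level or interval for the repeated analysis, or says which patency analysis decides the hypothesis. Section 10 lists one report of patency, placed after six-month follow-up of all patients, and a later report of PTS.

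**The concern.** The second patency analysis is not a fresh test. It contains the first 100 patients and adds about 100 more, so the same null hypothesis gets two correlated chances of rejection. If both are judged at 5%, the chance of at least one false rejection exceeds 5%.

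The first look cannot simply be presumed descriptive. The sentence before it says 76 patients suffice to test the hypothesis, so an analysis on 100 reads as a powered test. What is at stake is a patency claim made at 100 patients, or made at 200 after a non-significant first look, with a nominal p-value or 95% interval that overstates the evidence.

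**Working it through.** **Inputs**
- Patency 50% v 80%, alpha 5%, power at least 80%, 76 patients: section 8.1.
- PTS 25% v 10%, alpha at most 5%, power at least 80%, about 100 per group: section 8.1.
- Looks at 100 and 200 patients: section 8.1. With equal groups that is 50 and then 100 per arm, at information fractions 0.5 and 1.
- Sidedness is not stated. Two-sided is assumed, because 95% limits are planned and the PTS figure reproduces only that way (a one-sided test gives 79 per arm, or 92 with continuity correction).
- Correlation between the patency and PTS test statistics is not given. It is varied below.

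**1. The plan's own sample sizes**

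Pooled two-proportion formula: n per arm = [1.96·√(2p̄(1−p̄)) + 0.8416·√(p₁(1−p₁)+p₂(1−p₂))]² / (p₁−p₂)².
- PTS, p̄ = 0.175: 2.2397 / 0.0225 = 99.5, so 100 per arm. This matches.
- Patency, p̄ = 0.65: 3.4632 / 0.09 = 38.5, so 39 per arm, 78 in total. The arcsine formula gives 2 × 7.849 / 0.6435² = 37.9, so 38 per arm, 76 in total, which matches exactly.

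Each hypothesis is therefore sized at its own full two-sided 5%.

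**2. Type I error for patency over two looks**

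Under the null, Z₁ (100 patients) and Z₂ (200 patients) are bivariate normal with correlation √(100/200) = 0.707.
- P(|Z₁| ≤ 1.96 and |Z₂| ≤ 1.96) = 0.9169.
- P(rejection at either look) = 1 − 0.9169 = 0.0831, or **8.3%**.

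A binomial simulation with the uncorrected chi-square test and common patency rates of 0.5, 0.65 and 0.8 gives 9.3%, 8.2% and 8.6%, so the normal approximation is adequate.

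**3. Context: patency and PTS counted together**
- Independent outcomes: 1 − 0.9169 × 0.95 = 12.9%.
- Correlation 0.3, 0.5, 0.7, 0.9 (simulation): 12.6%, 12.1%, 11.4%, 10.1%, falling towards 8.3% as the correlation approaches 1.
- Only the 200-patient patency test counts, outcomes independent: 1 − 0.95² = 9.75%.

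**4. Power of the patency test at 50% v 80%**

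Power = Φ[(0.30 − c·√(2 × 0.65 × 0.35/n)) / √(0.41/n)], with n per arm and critical value c.

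| Look | c | Power |
|---|---|---|
| 100 patients (n = 50), unadjusted | 1.960 | Φ(1.248) = 89% |
| 200 patients (n = 100), unadjusted | 1.960 | Φ(2.620) = 99.6% |
| 100 patients, O'Brien-Fleming | 2.797 (p<0.005) | Φ(0.366) = 64% |
| 200 patients, O'Brien-Fleming | 1.977 (p<0.048) | Φ(2.603) = 99.5% |

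The O'Brien-Fleming pair put into the calculation of step 2 gives an overall 5.0%.

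**The case against.** The best defence is that the 100-patient analysis may never have been meant to carry a claim. Section 8.1 attaches no stopping rule or decision to it, recruitment continues for PTS whatever it shows, and section 10 schedules a single patency report after all patients have six months of follow-up. If only the 200-patient result counts, patency is tested at 5% and nothing is inflated. That reading is possible, but section 8.1 does not say it, and the powered-at-76 sentence points the other way. The 8.3% is therefore conditional on either look counting.

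A second defence is that interim boundaries are often left to a statistical analysis plan, which is not at hand. That is fair for the detail of a boundary. Here, however, the protocol itself fixes the level, the number of looks and their timing, and these do not fit together if both looks are tests.

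A reader might go further and infer that the trial's overall false-positive rate is 12–13% against a stated 5%. The documents do not support that. They give 5% as the level for each hypothesis, never as a joint guarantee, and they do not define success as a result on either outcome. Section 2 even describes the major outcome as PTS in relation to early patency. The figure also needs low to moderate correlation between the outcomes. The documents give no correlation, and the trial's rationale suggests the two are related.

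**Conclusion.** The point holds for patency. As written, section 8.1 allows two unadjusted tests of one hypothesis at 5%, and the resulting type I error is 8.3% (8.2–9.3% in the binomial check). This assumes two-sided tests, equal groups, looks at exactly half and full information, and that significance at either look would be claimed. The PTS test is unaffected.

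The joint figure, 12.9% under independence and falling towards 8.3% with rising correlation, describes a claim that the protocol does not make and is not a finding in itself. With no stopping decision tied to the first look and an almost free remedy, this is a should-fix.

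**What to change.** In section 8.1, choose one of two statements:

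1. **Preferred.** The analysis at 200 patients is the confirmatory test of 6-month patency, at two-sided 5%. The analysis of the first 100 is descriptive and supports no claim of efficacy.
2. **If a claim at 100 patients is wanted.** Patency is tested with O'Brien-Fleming bounds, about p<0.005 at 100 and p<0.048 at 200, for an overall two-sided 5%.

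Add one sentence saying that patency and PTS are separate hypotheses, each tested at 5%, with no claim of joint 5% control.

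Cost: a few sentences and no extra patients. Option 1 gives up any formal claim at 100 patients and keeps 99.6% power at 200. Option 2 lowers power at the first look from 89% to about 64% and leaves it above 99% at 200, under the protocol's assumed rates. The PTS test, its level and its sample size are unchanged.

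Joint control across the two outcomes would be a separate trade-off and is not needed to repair this fault. Testing PTS only after a significant patency result would make the outcome that drives the 100 per group depend on patency; at 100 per arm that gate has only 57% power if patency after catheter-directed thrombolysis is 65% rather than 80%. A split of 1% for patency and 4% for PTS would cut PTS power to 77%, below the 80% stated.
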